## 2.2 Study Rationale

Coronary heart disease (CHD) is the leading cause of premature morbidity and mortality in the United States, including in patients with diabetes. In 2012 there were 29.1 million diabetic patients in the US, including 27% of people age 65 or older. Of these, 6.4 million had coronary artery disease (CAD) and could potentially be eligible for the therapy to be tested in this application. Despite medical research advances that have identified effective medical therapy to reduce coronary events in diabetes, 68% of the 223,000 diabetic patients who died in 2012 had heart disease as either the principal or contributing cause. Compared with non-Hispanic whites, the risk of diagnosed diabetes is 70% higher among African Americans and 80% higher among Hispanics. Although we do not fully understand the mechanism of chelation benefit and how it possibly relates to risk of diabetic patients, the chelation strategy diabetic patients had their risk of major adverse cardiovascular events reduced to the level of those patients who did not have diabetes. Chelation, in other words, appeared to lower the risk of diabetes for cardiovascular events to the non-diabetic post-MI patient level. This finding alone has potentially major public health implications. From an economic perspective, diabetes is a costly disease that consumes a large proportion of the national health care budget. In the US, 1 in 5 health care dollars is spent treating people with diabetes. The annual expenditure exceeds \$245 billion (B), including \$176B in direct costs and \$69B in indirect costs (disability, work loss, premature mortality). TACT2, if positive, will likely have major public health and scientific impact.

### Possible Benefit of Chelation Therapy

The epidemiologic evidence that many metals are toxic and promote cardiovascular disease is robust, particularly for lead and cadmium, metals chelated by the edetates. One possible hypothesis, which is an exploratory analysis within the present trial, is that edetate disodium-based chelation depletes body stores of ubiquitous toxic metal pollutants, lead and cadmium in particular, acquired from the environment over many years and that depletion of toxicants leads to improved outcomes.

### EDTA Pharmacology

The present trial requires intravenous administration of the test article, edetate disodium. This is supported by extensive literature demonstrating poor absorption from the gastrointestinal tract. Only 5-10% of an oral dose is absorbed in the body, 91% of an oral dose is recoverable from the feces, and 4% is recoverable from the urine. In blood, the drug is found in the plasma compartment. EDTA does not appear to penetrate cells; it is distributed primarily in the extracellular fluid with only about 5% of the plasma concentration found in the spinal fluid. The half-life of EDTA is 20 to 60 minutes. EDTA is excreted primarily by the kidneys, with about 50% excreted in one

hour and over 95% within 24 hours. Calcium and other chelates are excreted in the urine bound to the EDTA. Almost none of the compound is metabolized.

[figure not shown]
The biological effects of EDTA are due to the formation of chelates with divalent and trivalent metals. The stability of the metal-EDTA complex is directly related to its pH – the higher the pH, the more stable the chelate. Intravenous infusions of edetate disodium result in the chelation of ionized calcium. Transient but mild reduction of serum calcium can be observed following the slow intravenous infusion of EDTA, and was observed in TACT (below). 1gm of EDTA can effectively bind approximately 120 mg of calcium. Among metals normally found as trace metals and metals present pathologically, EDTA has been demonstrated to bind and promote the excretion of cadmium, lead, zinc, copper, iron, manganese, and vanadium. Virtually all of the metals chelated by EDTA are excreted in the urine within 24 hours. In the case of calcium, 28% is excreted during the infusion, 60% in the 6 hours following the infusion, and the remainder between 6 and 12 hours after. Among the essential metals chelated by disodium EDTA are copper and iron. Both of these metals have an important role in oxidative state and generally exist in an intracellular compartment or protein-bound. However, there is an important, non-protein bound component that may be chelated by EDTA salts. EDTA salts may promote the excretion of up to 10 mg/day of iron and increase urinary copper by almost 140%. The oral supplement regimen in TACT2 repletes copper. Iron was not substantially diminished by EDTA in TACT, and will be measured during the TACT2 infusion regimen.

### Preliminary data on metal excretion following a TACT2 infusion

A preliminary study measured metal excretion after one infusion of placebo, and one of active chelation. Twenty male participants (mean age 66, range 51 to 81) were recruited using the same criteria as in TACT (post-MI, age  $\geq 50$ , creatinine  $\leq 2.0$  mg/dL). Urinary concentrations of 20 toxic metals (Al, Sb, As, Ba, Be, Bi, Cd, Cs, Gd, Hg, Pb, Ni, Pd, Pt, Te, Tl, Th, Sn, W, U) normalized to creatinine excretion were measured at baseline, for 6 hours following a placebo infusion of 500 mL normal saline and 1.2% dextrose, and for 6 hours following a 3 gram edetate disodium-based infusion as used in TACT.

Following an edetate disodium-based TACT infusion, there was a striking increase in the urinary excretion of lead (mean 3,926% increase,  $P < 0.001$ ; Figure A), cadmium (739% increase,  $P < 0.001$ ; Figure B), and nickel (131% increase,  $P < 0.001$ ). There was also a modest increase in the urinary excretion of tin and thallium (30-40%;  $P < 0.05$ ). These preliminary data show that

Effect of Placebo or Edetate disodium-based infusion on urinary lead (A) and cadmium (B) excretion\*

\*Lines represent individual patient data points. Bar graphs are mean  $\pm$  SD of % change from baseline.

an edetate disodium-based infusion, identical to that used in TACT and proposed for TACT2, markedly increased excretion of lead and cadmium. Whether enhanced excretion of metals following repeated chelation infusions leads to a reduction in blood lead or pre-infusion urine cadmium (reflecting total body stores of each) is unknown, but will be identified by TACT2.

#### **FDA safety information and labeling on edetate disodium**

Edetate disodium is an old drug for which no clear modern indication exists. Its current approval, as listed on the FDA website, is for medical conditions for which more modern, better treatments exist:

*“Edetate disodium is approved by the FDA for use in selected patients with high blood calcium levels (hypercalcemia) as well as for use among patients with heart rhythm problems due to intoxication with the drug, digitalis.”*

Edetate disodium has a long safety record, which was reviewed by FDA in 2007. Between 1971 and 2007, a time period during which hundreds of thousands of doses of edetate disodium were likely used, there were 11 deaths reported to FDA associated with the use of edetate disodium. According to FDA, 7 of 11 deaths resulted from confusion of edetate disodium with another drug, and hence its misadministration, either with too high a dose or more commonly as an IV push rather than a slow infusion. Thus, in a period spanning 36 years, there were 4 deaths associated with edetate disodium, in which edetate disodium was not misused by being confused with a different drug. This is consistent with the safety data for TACT presented below.

#### **Safety of EDTA chelation as reported in TACT**

We amassed a substantial body of safety data in TACT. EDTA was associated with few side effects and there were no differences in serious adverse events compared with placebo. Some of the safety specifics are summarized below.

- **Calcium.** Hypocalcemia, defined as a calcium level less than 8.5 mg/dL prior to an infusion, was reported in 52 chelation patients (6.2%) and 30 placebo patients (3.5%) (P=0.008). One patient, non-diabetic, had symptomatic hypocalcemia associated with muscle cramping that led to an emergency department visit. With regards to bone health, there were 2 fractures in the patients receiving the full chelation strategy and 2 fractures in those receiving double placebo (P=1.00). Although no safety signal pertaining to bone health was found in TACT, the effect of chelation on calcium makes it appropriate to measure calcium during the infusion period, as well as designate fractures as an event of interest and specifically query for it at regular intervals in the clinic visits and the telephone follow-up.
- **Kidney.** An abnormal creatinine during the infusion phase was reported in fewer 3/839 (0.4%) placebo patients than chelation 9/868 (1%) patients (P=0.093). Because EDTA is renally excreted, creatinine will be followed during the infusion period. Vitamin C in high doses has been associated with oxalate kidney stones, and this was a rare complication in TACT.

- **Liver.** There were no significant differences in liver enzyme abnormalities in the chelation compared with the placebo group. Liver function will therefore not be monitored after the screening study.
- **Hematology.** There were no significant differences in abnormalities of hematologic parameters (white blood cells, hematocrit, and platelet count) in EDTA compared with placebo groups. Complete blood counts will be assessed at screening, infusion 20, and at the end of the infusion period or 1 year.
- **Hypoglycemia.** There was 1 episode of hypoglycemia reported in TACT, not clearly caused by the infusion. Because diabetic patients in TACT2 may possibly have hypoglycemic events due to the treatment of their diabetes, we have retained this potential adverse event in the ICF.
- **Death.** There were 2 deaths attributed by the blinded Medical Monitor as possibly or probably due to study therapy: 1 in the edetate disodium group and 1 in the placebo group. This potential adverse effect has been retained in the ICF.

**Safety – chelation infusions in the population with diabetes:** In the patients with diabetes, chelation was as safe as in the non-diabetic population. There were 95 serious adverse events (non–endpoint events) in the population with diabetes mellitus (56 chelation placebo and 39 chelation active).

**Safety – Oral multivitamins and multiminerals:** Serious adverse events occurred in 124 (15%) vitamin recipients and 103 (12%) placebo recipients (difference, 3 percentage points [95%CI=0.7 to 5.7 percentage points]). Adverse events included 12 (1.4%) incident neoplasms in the vitamin group and 11 (1.3%) in the placebo group (difference, 0.1 percentage point [95%CI= 0.8 to 1.3 percentage points]). No evidence suggested harm from vitamin therapy in any category of adverse events.

### 3. STUDY DESIGN

TACT2, like TACT, is a 2X2 double-blind, placebo-controlled multicenter international (US and Canada) factorial trial testing 40-weekly edetate disodium-based chelation infusions and twice daily OMVM. On December 31, 2020, TACT2 completed enrollment. The study enrolled 1000 diabetic patients 50 years of age or older with a prior MI and a serum creatinine of 2.0 mg/dL or less. The factorial design was selected for TACT2 because it replicates the TACT design and it provides the most information about the independent contributions of the chelation and OMVM factors. Patients will be randomly allocated (1:1:1:1) to 4 factorial groups:

1. Active chelation + active OMVM
2. Active chelation + placebo OMVM
3. Placebo chelation + active OMVM
4. Placebo chelation + placebo OMVM

Patients will be followed for clinical events until the beginning of the analysis phase, 3 months before the end of the 5-year trial. During the infusion period, patients will have frequent clinical and laboratory monitoring to determine whether a clinical endpoint has

been reached, to assess study safety, and to obtain biosamples for the exploratory analyses of metal excretion, and to establish the biorepository. Starting 6 months after randomization, patients will be followed by telephone from the DCRI Call Center. The combination of early clinic visits and samples, combined with later telephone follow-up will permit the ascertainment of clinical and laboratory goals in TACT2, as listed below and in greater detail in Section 6.1.

The primary objective of TACT2 is to determine if the chelation-based strategy increases the time to the first occurrence of any of the components of the TACT2 primary endpoint: all-cause mortality, myocardial infarction, stroke, coronary revascularization, or hospitalization for unstable angina compared to the placebo chelation strategy.

The secondary objectives of TACT2 are to determine:

1. if the chelation-based strategy reduces the overall rate of occurrence of the events which define the primary TACT2 endpoint: all-cause mortality, myocardial infarction, stroke, coronary revascularization, or hospitalization for unstable angina events compared to placebo chelation strategy.
2. to determine if the chelation-based strategy increases the time to the first occurrence of a combined secondary endpoint: cardiovascular mortality, recurrent myocardial infarction, or stroke compared to placebo chelation strategy.
3. to determine if the chelation-based strategy increases the time to all-cause mortality compared to placebo chelation strategy.

Additional analyses, defined as those seeking to confirm a signal of benefit observed in TACT, or to develop mechanistic hypotheses for benefits of chelation expected in TACT2, include:

- i. Analysis of the primary endpoint in patients receiving OMVM compared with oral placebo to determine whether the signal of OMVM benefit is reproduced
- ii. Analysis of the primary endpoint in patients receiving active chelation + active OMVM, compared with placebo chelation + placebo OMVM to determine if combination therapy has a greater effect size, as observed in TACT
- iii. Analysis of markers of diabetes (fasting glucose, HbA1c, microalbuminuria) throughout the infusion regimen to determine whether changes in diabetes control or microvascular effects may be associated with the TACT2 results
- iv. Analysis of lead and cadmium levels collected at multiple times during the infusion regimen to assess whether toxic metal removal is associated with the TACT2 results
- v. Collection of a specimen biorepository to permit future analyses yet to be conceived

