### **9.2 Sample Size and Randomization**

Participants will be randomized in a 1:1:1:1 allocation ratio using simple randomization. The study was originally designed to enroll a total of 1200 participants with a minimum follow-up of 12 months. The DSMB conducted a blinded review of enrollment aggregate event rates, and projected event rates in July 2019. Following this blinded review, the

DSMB recommended a reduction in the target sample size to 1100 participants and an increase in the minimum follow-up from 1 year to approximately 2.5 years. Due to slowed enrollment related to the COVID-19 pandemic, in the fall of 2020, the DSMB and the NIH leadership agreed to a proposal to complete enrollment by 12/31/2020 with an allowance to follow the study participants until there are enough primary endpoint events to maintain 85+% power.

Several design factors and research objectives have been considered in developing an appropriate sample size for the TACT2 study. First, patient enrollment and follow-up has been determined so there would be a sufficient number of endpoints to provide a high degree of confidence for testing the primary hypothesis. Second, the statistical power for secondary endpoints has been considered. Finally, the sample size has been determined to provide a reasonable level of confidence for detecting clinically important differences in outcome between treatment strategies even if current projections of event rates and hypothesized differences in clinical outcomes between the treatment groups prove to be optimistic.

Table 3 shows the required number of endpoint events to have 80% to 90% power with hazard ratios varying from 0.50 to 0.75. The two factors (EDTA chelation and OMVM) are assumed to be additive for the sample size calculations. Based on TACT we anticipate a hazard ratio of 0.70 (active chelation vs. placebo chelation) to determine the sample size requirements. This hazard ratio assumption is very conservative compared to the observed effect in TACT. Assuming a two-sided 0.05 type I error rate and approximately 5% consent withdrawal or loss-to-follow-up per year, the final sample size of 1000 participants will provide approximately 85% power to detect a hazard ratio of 0.70 for the primary endpoint of time to all-cause mortality, myocardial infarction, stroke, coronary revascularization, or hospitalization for unstable angina comparing active chelation vs. placebo chelation.

Table 3. Required number of events						

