	HR=0.50	HR=0.55	HR=0.60	HR=0.65	HR=0.70	HR=0.75
80% power	65	88	120	169	247	379
85% power	75	100	138	194	282	434
90% power	87	118	161	226	330	508

Calculations performed using nQuery 7.0 and assume a 0.05 type I error rate (two-sided) with 1:1 randomization.

For other exploratory endpoints, we outline a general power justification for comparisons to be made among the four arms of the 2x2 factorial design. We anticipate that roughly 1000 participants will have blood and urine samples available from baseline and one or more follow-up time points. A sample size of 250 participants per group will provide 80% or greater power for any between group differences greater than  $\frac{1}{4}$  of a standard deviation. These calculations are based on a two-sample t-test and assume a two-sided type I error rate of 0.05.

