## **9.6 Data Analyses**

### **Primary Endpoint Analysis**

The primary objective of TACT2 is to determine if the chelation-based strategy increases the time to composite of all-cause mortality, myocardial infarction, stroke, coronary revascularization, or hospitalization for unstable angina compared to the placebo chelation strategy. The statistical comparison will be based on the time from randomization to the first occurrence of all-cause mortality, myocardial infarction, stroke, coronary revascularization, or hospitalization for unstable angina. The Cox proportional hazards regression model will be used to assess outcome differences between the treatments. An initial Cox model will include indicator variables for the active chelation and active OMVM groups, an interaction term for the active chelation and active OMVM, age, sex, and use of insulin. If the interaction term for the active chelation and active OMVM is not statistically significant at the two-sided 0.05 level, the primary analysis will be based on a Cox model which includes indicator variables for the active chelation and

active OMVM groups, age, sex, and use of insulin. The chelation treatment effect will be summarized using hazard ratios and associated 95% confidence intervals. In addition to the statistical hypothesis testing, Kaplan-Meier survival estimates will be constructed based on the time from randomization to the first primary event occurrence.

The OMVM treatment effect from the Cox model will be estimated using the Cox model described above. Given the results of TACT and the focus on chelation therapy, the interpretation of the OMVM treatment effect will be considered exploratory.

Assessment of the proportional hazards assumption will be evaluated using visual analysis (of the survival and log {-log (survival)} functions), as well as tools within the “proportionality test” statement of Proc Phreg in SAS.

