### **Secondary Endpoint Analysis**

The analyses for the time-to-event secondary endpoints will be similar to those outlined for the primary endpoint using the time from randomization through the first occurrence of any component of a specific secondary endpoint (or censoring) as the response variable, and assessing group differences using the Cox proportional hazards model. The effect of the chelation treatment strategy vs. placebo chelation on these time-to-event secondary endpoints will be summarized using hazard ratios (with associated confidence intervals) computed from the Cox model. Kaplan-Meier curves will be constructed to display the cumulative event rates of the treatment groups.

To test the individual treatment strategies against the placebo chelation – placebo OMVM group, we will add three indicator variables to the Cox proportional hazards model described above.

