1.1 Study Design

The Trial to Assess Chelation Therapy 2 (TACT2) is a randomized, double blinded, placebo-controlled 2x2 factorial clinical trial. The study treatments are edetate disodium-based chelation (weekly infusion for 40 weeks) and high-dose oral multivitamins and multi-minerals (OMVM) (twice daily for up to 5 years). Subjects with diabetes mellitus with a prior myocardial infarction (MI) are recruited from participating sites in the US and Canada and randomized in a 1:1:1:1 fashion to 4 groups:

- i. Active chelation + active OMVM
- ii. Active chelation + placebo OMVM
- iii. Placebo chelation + active OMVM
- iv. Placebo chelation + placebo OMVM.

Patients will be followed for clinical events until the earlier of database lock or five years from randomization. Clinical outcomes will be collected by study sites at each infusion visit and by the DCRI Call Center at month 6 and 12, and every 4 months afterwards with the last assessment at month 60.

TACT2 is an event driven trial with a plan to continue until at least 282 primary endpoint events are identified. The original planned sample size was 1200 participants. The sample size was later modified to 1100. The final enrollment is 1000, but with an increased follow-up time to preserve statistical power. More details on sample size and power calculation are included later in the SAP.

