3.2.1 Primary Analysis

The primary objective is to determine if the chelation-based strategy increases the time to composite endpoint compared with the placebo chelation strategy. The primary composite endpoint will be analyzed using a Cox proportional hazards regression model of time from randomization to the first occurrence of all-cause mortality, MI, stroke, coronary revascularization, or hospitalization for unstable angina.

The primary analysis will be based on a Cox model which includes indicator variables for the active chelation as the primary variable of interest and active OMVM groups, age, sex, and baseline insulin use as covariates. Age will be included in the model in the form of cubic splines using three knots at 10th, 50th, and 90th percentiles. Two separate manuscripts will explore the effect of active OMVM and the effects of chelation by OMVM.

The chelation treatment effect will be summarized using hazard ratios and associated 95% CIs. A hazard ratio of < 1 would suggest a benefit for the chelation-based therapy. Kaplan Meier survival estimates will be constructed based on the time from randomization to the first

primary event occurrence. Events occurring after withdrawal of consent or informed consent expiration will be censored.

The OMVM treatment effect from the Cox model will be estimated using the Cox model described above. A hazard ratio of < 1 would suggest a benefit for OMVM treatment. Given the focus on chelation therapy, the interpretation of the OMVM treatment effect will be considered exploratory. A full set of analyses of the 2x2 design will be reported in a separate manuscript.

Four interim analyses were conducted at 25%, 40%, 60%, and 80% of expected information using a Haybittle-Peto-type boundary for efficacy (i.e. $p \leq 0.001$, $Z=3$). For this reason, the adjusted two-sided significance level for the final analysis is 0.05 (i.e., the corresponding critical value, $Z = -1.96$).

Formal statistical hypothesis testing will follow a hierarchy based on statistical significance of the prior endpoint. If the prior endpoint is statistically significant at the 0.05 level, the next endpoint's p-value will be tested for significance. The outcome hierarchy will be evaluated as follows:

- 1) Primary composite outcome
- 2) Secondary all-cause mortality outcome (with conservative censoring)
- 3) Secondary composite outcome of cardiovascular mortality, MI, or stroke

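### Comparing both active treatments with double placebo cannot show that the combination exceeds chelation alone, and the model for the single strategies has redundant treatment terms (minor, exploratory)

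*Protocol*

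**What the plan says.** Three places bear on the point.

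- **The combination question.** Protocol section 3, item ii, sets active chelation plus active OMVM "compared with placebo chelation + placebo OMVM to determine if combination therapy has a greater effect size, as observed in TACT". The Précis and section 1.2 list the same contrast as exploratory, without that stated aim. Item i of the same lists compares OMVM with oral placebo.
- **The model for the single strategies.** Protocol 9.6, Secondary Endpoint Analysis, says that to compare each strategy with double placebo "we will add three indicator variables to the Cox proportional hazards model described above". The model described in Primary Endpoint Analysis already contains a chelation indicator and an OMVM indicator and, initially, their interaction.
- **The interaction.** Protocol 9.6 checks it first: "If the interaction term for the active chelation and active OMVM is not statistically significant at the two-sided 0.05 level, the primary analysis" uses the main-effects model. SAP 3.2.1 goes straight to the main-effects model and states: "Two separate manuscripts will explore the effect of active OMVM and the effects of chelation by OMVM". SAP 3.4 does not list OMVM assignment among the subgroups.

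Protocol 9.2 assumes that the two factors act additively. Protocol 2.1 regards no OMVM effect as the most likely result.

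**The concern.** A greater effect has to be greater than something. Table 1 of the protocol shows what is meant: for TACT it puts chelation vs placebo (18% overall, 41% in diabetes) beside the combination vs double placebo (26% and 51%), and the text after it reads the gap as what OMVM adds. No interval is attached to that gap. The contrast in item ii compares the two extreme cells, so it contains the chelation effect whether or not OMVM does anything. A favourable result there could be read as support for the combination over chelation alone when it carries no such information.

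The model sentence is a separate, technical matter. With redundant terms, what a printed coefficient means depends on which terms the software drops.

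The third matter is visibility. The primary HR averages over OMVM assignment. Section 2.1 of the protocol values the factorial design because it could support chelation without vitamins, yet the primary manuscript as planned would not show the chelation HR among patients on placebo OMVM.

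**Working it through.** **Inputs.** Two-sided alpha 0.05 and 1:1 allocation (protocol Table 3: "Calculations performed using nQuery 7.0 and assume a 0.05 type I error rate (two-sided) with 1:1 randomization"); design HR 0.70 (protocol 9.2); at least 282 events (SAP 1.1); four equal cells of about 250 (Précis); projected placebo rate 10.4% per patient-year (SAP Table 2), used only to split events over cells.

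**1. The plan's own figure.** Schoenfeld: events = 4(1.960 + 1.036)² / (ln 0.70)² = 4 × 8.98 / 0.1272 ≈ 282.3, which is 283 rounded up, against 282 stated. Power with 282 events: Φ(0.357 × √282 / 2 − 1.96) = Φ(1.035) = 85.0%. The plan's sizing reproduces.

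**2. What the item ii contrast estimates.** Under additivity, log HR(both active vs double placebo) = log HR(chelation) + log HR(OMVM). With inert OMVM and chelation HR 0.70 this is ln 0.70 + 0, so the HR is 0.70, the same as for chelation alone.

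**3. Its power for that real effect.** Half the events, about 141, fall in these two cells.
- Equal-split formula: Φ(0.357 × √141 / 2 − 1.96) = Φ(0.16) ≈ 56%.
- With 282 events split under exponential hazards, the placebo-chelation cells have about 81 events each and the active-chelation cells about 60 each. SE = √(1/81 + 1/60) = 0.170, power about 55%.
- Simulation (400 trials): 58.5%, with Monte Carlo SE √(0.585 × 0.415 / 400) = 2.5 percentage points.
- At the TACT diabetes HR of 0.59: about 86%.

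**4. Informal comparison with the chelation main effect.** Write l for the log hazard in a cell, with the first letter for chelation and the second for OMVM (A active, P placebo). Then

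(l_AA − l_PP) − ½[(l_AA − l_PA) + (l_AP − l_PP)] = ½[(l_AA − l_AP) + (l_PA − l_PP)],

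which is the OMVM main effect. If OMVM is inert, the combination looks better than the chelation main effect in about half of trials by chance.

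**5. Precision of the quantities that answer the question.**

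| Quantity | Events | SE of log HR | Power at HR 0.89 |
|---|---|---|---|
| OMVM main effect (additivity) | 282 | 2/√282 = 0.12 | about 16% |
| Both active vs active chelation + placebo OMVM | 116 to 120 | 2/√116 = 0.186; √(2/60) = 0.183 | about 9 to 10% |
| Interaction ratio | 282 | 4/√282 = 0.238; 0.241 with the 81/60 split | not applicable |

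The 116 is 282 × 0.7/1.7; the 120 comes from the exponential split. HR 0.89 is the 11% OMVM reduction reported for TACT in protocol 2.1. The 95% CI for the second row is the estimate multiplied and divided by exp(1.96 × 0.186) = 1.44.

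**6. Rank of the strategy model.** Let C and O be the factor indicators, and let a, b and d mark the chelation-only, OMVM-only and both-active cells. Then C = a + d and O = b + d: two exact dependencies among five columns, so rank 3. If the interaction is kept, it equals d, giving six columns and still rank 3. In a simulated Cox fit with five columns, two eigenvalues of the information matrix were zero to rounding, the fit did not converge, and the standard errors were above 3 million or undefined. If software keeps C, O and a, and drops b and d, the coefficient on a is minus the interaction, not chelation-only vs double placebo. The three cell indicators alone have rank 3 of 3 and fit normally.

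**The case against.** The case for leaving the text alone is substantial, and much of it stands.

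- **What OMVM adds is already estimated.** Item i does this, and the Cox models in protocol 9.6 and SAP 3.2.1 give the OMVM effect. Under additivity that estimate is more precise than the contrast within active chelation (SE 0.12 against 0.19). This stands, and it belongs in the fix. But neither document ties it to item ii.
- **The 56% is not an error rate.** A reader might infer that the plan would falsely declare the combination effective in 56% of trials. The documents do not support that. With chelation HR 0.70, the combination truly beats double placebo, and no test threshold or claim is attached to item ii.
- **The strategy comparisons are not lost.** A reader might infer that they cannot be estimated. Only the individual coefficients are undetermined. The contrasts with double placebo survive as linear combinations, and three indicators are the right number for four cells. The fault is one verb. The sentence also sits under secondary endpoints while item ii concerns the primary one, although 9.6 models both in a similar way.
- **The factorial analysis is not abandoned.** SAP section 1 limits that document to the primary chelation manuscript, and 3.2.1 defers the 2x2 analyses to separate papers. Not using an interaction test to choose the primary model is also defensible.
- **Replication.** Repeating the TACT display is a reasonable descriptive choice.

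None of this makes the extreme-cell contrast answer the question that section 3 puts to it, or makes the model full rank as written.

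**Conclusion.** The point holds as a minor one, confined to exploratory analyses. The item ii contrast is a total effect of both factors and cannot show that the combination exceeds chelation alone. The model sentence in protocol 9.6 gives five treatment terms of rank 3. In addition, the SAP's primary model leaves out the protocol's interaction check, and the primary manuscript would carry no chelation HR by OMVM assignment.

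The primary test, the 282-event target, the testing hierarchy and the monitoring of chelation are untouched. A reader might infer that the Précis and section 1.2 need the same correction. They do not, because they list the contrast without the greater-effect aim.

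The contrast result rests on the protocol's additivity assumption. The event splits and power figures also rest on equal cells, exponential hazards and the 10.4% placebo rate. The rank result needs none of these.

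**What to change.** - **Protocol section 3, item ii only.** Judge whether the combination has a greater effect by three estimates with 95% CIs: the OMVM main effect (under additivity), both active vs active chelation + placebo OMVM, and the interaction ratio. Keep both active vs double placebo as a descriptive total effect.
- **Protocol 9.6, strategy comparisons.** State that the three group indicators replace the chelation and OMVM indicators and any interaction term.
- **SAP 3.2.1 and 3.4.** In the primary manuscript, report the chelation HR within placebo OMVM and within active OMVM, and the interaction ratio with its 95% CI. Present these descriptively and not as a gate for the primary model, and reconcile this with the interaction check in protocol 9.6.

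The cost is a few sentences and one extra table from data already collected. The drawback is wide intervals: the trial has little power for what OMVM adds to chelation, and the table will show that.
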